### 5.5.3. Prohibited and/or Restricted Treatments

Pre-medications should not be administered routinely prior to dosing of study drugs.

Subjects are prohibited from receiving the following therapies and treatments during the study:

- Immunotherapy not specified in this protocol
- Chemotherapy
- Investigational agents other than GS-4224
- Corticosteroids for any purpose other than to modulate symptoms from an irAE, or for use as a premedication in subjects with a known history of hypersensitivity reactions (ie, IV contrast for imaging)

**Note:** Systemic corticosteroid dose of prednisone 10 mg daily or equivalent is permitted while on study

**Note:** Use of intraocular, intranasal, inhaled, or topical corticosteroid is permitted

- Bisphosphonates and/or receptor activator of nuclear factor kappa-B ligand (RANKL) inhibitor therapies should be initiated if indicated before informed consent has been signed. These therapies may be continued if treatment with an agent from one of these 2 classes was initiated **prior** to signing informed consent.
- Subjects who, in the assessment by the investigator, require the use of any of the aforementioned treatments for clinical management should be removed from the study.
- There are no prohibited therapies during the Posttreatment Follow-up Phase.

#### **5.5.4. Other Restrictions and Precautions**

The following nondrug therapies must not be administered or performed during the study

- Major elective surgery
- Herbal remedies with immunostimulating properties (eg, mistletoe extract) or that are known to potentially interfere with major organ function (eg, hypericin)

Subjects should not abuse alcohol or other drugs during the study.

#### **5.6. Accountability**

The investigator is responsible for ensuring adequate accountability of all used and unused study drug. This includes acknowledgment of receipt of each shipment of study drug (quantity and condition). All used and unused study drug dispensed to subjects must be returned to the site.

Each study site must keep accountability records for GS-4224 that capture:

- The date received and quantity of study drug kits
- The date, subject number, and the study drug kit number dispensed
- The date, quantity of used and unused study drug kit returned, along with the initials of the person recording the information.

#### **5.7. Investigational Medicinal Product (IMP) Return or Disposal**

Gilead recommends that used and unused study drug supplies be returned to the shipping facility from which it came for eventual destruction. The study monitor will provide instructions for return. If return is not possible, the study monitor will evaluate each study center's study drug disposal procedures and provide appropriate instruction for destruction of unused study drug supplies. If the investigator has an appropriate standard operating procedure (SOP) for drug destruction as determined by Gilead, the site may destroy used (empty or partially empty) and unused study drug supplies in accordance with that site's approved SOP. A copy of the site's approved SOP will be obtained for the trial master file.

If study drug is destroyed on site, the investigator must maintain accurate records for all study drug destroyed. Records must show the identification and quantity of each unit destroyed, the method of destruction, and the person who disposed of the study drug. Upon study completion, copies of the study drug accountability records must be filed at the site. Another copy will be returned to Gilead.

The study monitor will review study drug supplies and associated records at periodic intervals.

## 6. STUDY PROCEDURES

The study procedures to be conducted for each subject enrolled in the study are presented in tabular form in [Appendix 2](#) and described in the text that follows.

The investigator must document any deviation from protocol procedures and notify the sponsor or contract research organization (CRO).

### 6.1. Subject Enrollment and Treatment Assignment

Entry into screening does not guarantee enrollment into the study. In order to manage the total study enrollment, Gilead, at its sole discretion, may suspend screening and/or enrollment at any site or study-wide at any time. It is the responsibility of the investigator to ensure that subjects are eligible to participate in the study prior to enrollment and continue to remain eligible throughout the study.

### 6.2. Pretreatment Assessments

#### 6.2.1. Screening Visit

Subjects will be screened within 28 days prior to the first dose of study drug to determine eligibility for participation in the study. The following will be performed and documented at screening:

Within 28 days prior to the first dose of study drug:

- Obtain written informed consent
- Obtain medical and medication history
- Complete physical examination including vital signs, body weight, and height
- Obtain blood samples for serum pregnancy and biomarkers
- Perform 12-lead electrocardiogram (ECG)
- Perform computed tomography (CT) scan with contrast or magnetic resonance imaging (MRI). For subjects with cHL, positron emission tomography-computed tomography (PET-CT) will also be performed. Baseline scans within 6 weeks of Cycle 1 Day 1 are acceptable.
- Assess ECOG performance status
- For the 1000 mg BID dose escalation cohort, CCI [REDACTED] the Phase 2 Dose Expansion cohort, determine level of tumor PD-L1
- For the Phase 2 Dose Expansion cohort, collect archival tumor sample or, alternatively, consent for an additional pretreatment tumor biopsy.

Within 10 days prior to the first dose of study drug:

- Obtain blood sample for chemistry and hematology

Subjects meeting all of the inclusion criteria and none of the exclusion criteria will return to the clinic within 28 days after screening into the study.

The investigator or qualified designee must obtain documented informed consent from each potential subject prior to participating in the clinical study.

After a subject signs an informed consent form (ICF), the subject will be assigned a unique, sequential subject number. Once a number is assigned, it cannot be reassigned if the original subject is found to be ineligible or withdraws consent.

All subjects will be given an Emergency Medical Support and Subject Card identifying them as participants in a research study. The card will contain study site contact information (including direct telephone numbers) to be utilized in the event of an emergency. The investigator or qualified designee will provide the subject with an Emergency Medical Support and Subject Card immediately after the subject provides written informed consent.

Subjects who fulfill all of the inclusion criteria and none of the exclusion criteria will be enrolled into the study. Subjects who do not meet any of the inclusion criteria or meet any of the exclusion criteria will be considered screen fails, and their demographic information and reason for screen failure should be documented.

Screening procedures are to be completed within the windows detailed below and prior to the first dose of study treatment:

During the screening period, attention must be given to washout periods for prior treatments and prohibited medications.

Results from assessments performed during the initial screening period are acceptable in lieu of repeating a screening test if performed within the specified period and the results meet the inclusion/exclusion criteria.

From the time of obtaining informed consent through the first administration of study drug, record all serious AEs (SAEs), as well as any AEs related to protocol-mandated procedures on the AEs case report form (CRF/eCRF). All other untoward medical occurrences observed during the screening period, including exacerbation or changes in medical history are to be captured on the medical history CRF/eCRF. See Section 7 (Adverse Events and Toxicity Management) for additional details.

Subjects' eligibility will be determined by results received from the central lab. If time constraints do not allow for timely processing of tests through central lab then eligibility may be determined using local lab results, with documentation of local lab results and sponsor approval. PD-L1 expression may be performed using a central or local laboratory.

## **6.2.2. Re-screening Criteria**

Subjects who do not enroll within 28 days of screening will be screen failed.

Re-screening may be allowed. Subjects who are re-screened after 28 days must be reconsented with a new screening number and the screening assessments must be repeated, as applicable. For subjects that are re-screened within 28 days, assessments with results that would exclude the subject will need to be repeated except for CT/MRI and/or PET-CT scans performed within 6 weeks of C1D1 and screening biomarker samples.

## **6.2.3. Baseline Assessments and Medical History**

A medical history will be obtained by the investigator or qualified designee. Medical history will include all active conditions; history of HBV, HCV, HIV, and/or human papilloma virus; and any condition diagnosed within the prior 10 years that is considered to be clinically significant by the investigator. Medical history will also include an assessment of smoking history.

Baseline symptoms will be assessed for each subject at screening. Baseline symptoms will be graded and recorded according to NCI-CTCAE version 5.0. Baseline symptoms will be characterized in terms including seriousness, causality to previous treatment, toxicity grading, and action(s) taken if any.

### **6.2.3.1. Cancer Disease Details and Prior Treatment**

Cancer disease history will be recorded separately and not listed as medical history. Current cancer disease details and prior treatment will be obtained for all subjects including:

- Detailed history of the tumor, including histopathological diagnosis, grading, and staging in accordance with the eighth edition of the American Joint Committee on Cancer staging manual (AJCC-8) Tumor Node Metastasis (TNM) classification at diagnosis
- All therapy used for prior treatment of the tumor (including surgery, radiotherapy, chemotherapy, and immunotherapy)
- Any other conditions treated with chemotherapy, radiation therapy, or immunotherapy
- Current cancer disease status
- Relevant somatic or germ line mutations detected
- Chronic viral infection, status if available
- Tumor markers if indicated

#### **6.2.4. Physical Examination Including Height and Weight**

The investigator or qualified designee will perform a complete physical exam during the screening period and at the EOT visit as per Schedule of Assessments and Procedures ([Appendix 2](#)). Beginning on C1D1, a modified physical exam will be performed to monitor for any changes (eg, lymph nodes, lung, cardiac, abdomen, skin, neurologic, and any systems, as clinically indicated).

For cycles that do not require a full physical exam per the Schedule of Assessments and Procedures ([Appendix 2](#)), the investigator or qualified designee will perform a modified physical exam as clinically indicated prior to study treatment administration.

Weight without shoes should be measured at each exam.

Height without shoes should be measured at screening only.

Clinically significant abnormal findings prior to the first dose of study drug should be recorded as medical history. After consent, new clinically significant abnormal findings should be recorded as AEs.

#### **6.2.5. Vital Signs**

The investigator or qualified designee will take vital signs at screening, prior to the administration of each dose of study treatment, and at the EOT visit as specified in the table of assessments in [Appendix 2](#). Vital signs will only be measured while subject is in seated or semi-recumbent position. Vital signs include temperature, pulse, respiratory rate, and blood pressure.

#### **6.2.6. Eastern Cooperative Oncology Group Performance (ECOG)**

ECOG performance status is an investigator assessment of the impact of the disease on the subject's activities of daily living. ECOG assessments will be performed at the time points listed in the Study Procedures Table ([Appendix 2](#)).

#### **6.2.7. Electrocardiogram**

A standard 12-lead ECG will be performed using local standard procedures at screening and at subsequent visits as specified in [Appendix 2](#). Clinically significant abnormal findings at screening should be recorded as medical history.

Subjects should rest quietly in the supine position for a minimum of 10 minutes prior to each scheduled ECG acquisition and should remain in that position until the recording is complete.

Where time points for ECG collection correspond to blood collection time points, ECGs should be acquired prior to blood collection.

There should be no environmental distractions (eg, TV, radio, conversation, etc.) while the subjects are resting prior to and during the recordings. Electrocardiograms will be recorded using the site's standard 12-lead ECG equipment. All ECGs will be obtained using instruments that analyze data using the same algorithms and produce the same data for interpretation. Electrode placement will be performed according to the method of Wilson, Goldberger, and Einthoven with a check to confirm that the augmented Vector Right (aVR) lead is not inverted.

The investigator or other qualified individuals at the study center will review ECGs to assess for changes in ECG intervals and morphology as compared to pretreatment ECGs.

#### **6.2.8. Prior and Concomitant Medications**

Prior medication taken by the subject within 30 days before starting the study will be recorded. In addition, record all treatments for a prior cancer other than current cancer even if taken greater than 30 days prior to Visit 1. Prior treatments for the current cancer will be recorded separately and not listed as a prior medication.

Concomitant medications, if any, taken by the subject during the study from the date of consent through the 30-day safety follow-up visit should be recorded. After the 30-day safety follow-up visit, all medications related to reportable SAEs will be recorded as defined in Section 7.

#### **6.2.9. Clinical Laboratory Assessments**

The central laboratory will be responsible for chemistry, hematology, coagulation, urinalysis, and serum pregnancy testing (per Table 6-1) as well as processing and/or storage of other study samples. Specific instructions for processing, labeling, and shipping samples will be provided in a central Laboratory Manual. The date and time of sample collection will be reported to the central laboratory.

If central laboratory results are not available, local laboratories may be used for dosing decisions. Local laboratory assessments resulting in a dose change or as part of an AE assessment, which is not supported by central lab results, will be reported on the eCRF. Gilead's standard reference ranges will be used.

Urine pregnancy test will be performed locally at the site.

Laboratory tests for screening (Table 6-1) should be performed within 28 days prior to the first dose of study treatment. After Cycle 1, predose laboratory procedures can be conducted up to 72 h prior to dosing.

Results must be reviewed by the investigator or qualified designee and found to be acceptable prior to each dose of study treatment. The report of the results must be retained as a part of the subject's medical record or source documents. Blood samples for study-related tests will be collected at time points specified in Appendix 2.

**Table 6-1. Analytes**

Chemistry	Urinalysis	Hematology	Other
Albumin	Color and appearance	WBC and differential count	Serum β–hCG or urine pregnancy test c Endocrine Function Tests TSH and freeT4 d Basal cortisol HIV, HBsAg, and HCV antibody viral testing in subjects with current or prior history of HIV, HBV, and HCV infection, respectively. b CD4+ count will also be performed in subjects with current or prior history of HIV.
Alkaline phosphatase	Specific gravity	Hemoglobin	
ALT	pH	Hematocrit	
AST	Occult blood	Platelet count	
Bicarbonate	Protein	ANC	
BUN/total urea	Glucose	MCH	
Calcium	Bilirubin	MCHC	
Chloride	Leukocyte esterase	MCV	
Serum Creatinine a	Nitrite	RBC	
GGT	Urobilinogen	Differential	
Glucose	Ketones	Eosinophils	
LDH	Microscopic b	Lymphocytes	
Lipase		Monocytes	
Cholesterol		Neutrophils	
Triglycerides		Coagulation	
Amylase		Prothrombin time (INR)	
Magnesium		aPTT	
Phosphorus/phosphates			
Potassium			
Sodium			
Total bilirubin b			
Direct bilirubin			
Total protein			

β hCG beta human chorionic gonadotropin; ALT alanine aminotransferase; ANC absolute neutrophil count; aPTT activated partial thromboplastin time; AST aspartate aminotransferase; BUN blood urea nitrogen; CD4+ cluster determinant 4 positive; Free T4 free thyroxine; GGT gamma glutamyltransferase; HBsAg hepatitis B surface antigen; HBV hepatitis B virus; HCV hepatitis C virus; HIV human immunodeficiency virus; INR international normalized ratio; LDH lactate dehydrogenase; MCH mean corpuscular hemoglobin; MCHC mean corpuscular hemoglobin concentration; MCV mean corpuscular volume; RBC red blood cell; TSH thyroid stimulating hormone; WBC white blood cell

a Estimated creatinine clearance (CLcr)/glomerular filtration rate will be calculated based on the Cockcroft Gault formula using actual body weight: CLcr (mL/min) (140 age [years])\* weight (kg) / (serum creatinine [mg/dL]\*72). If the subject is female, multiply the quantity by 0.85.

b Reflex testing based on other abnormalities

c Females of childbearing potential only. Serum pregnancy will be conducted at screening within 72 h of first treatment dose (if performed earlier in screening period then a urine pregnancy test may be performed prior to first dose); urine pregnancy test performed at all other indicated visits.

d TSH and free T4 will be tested by the central laboratory. T4 will be tested reflexively based on abnormal TSH results.

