#### 4.2. Inclusion Criteria

Subjects must meet all of the following inclusion criteria to be eligible for participation in this study. Additional indication-specific inclusion criteria for 1000 mg BID Dose Escalation Cohort and Phase 2 are provided in [Appendix 3](#).

- 1) Male or female  $\geq 18$  years of age
- 2) Dose Escalation Cohorts: Histologically or cytologically confirmed advanced malignant solid tumor that is refractory to or intolerant of all standard therapy or for which no standard therapy is available.
- 3) Dose Expansion and 1000 mg BID Dose Escalation Cohorts: Subjects must have available sufficient and adequate formalin-fixed tumor sample preferably from a biopsy of a tumor lesion obtained either at the time of or after the diagnosis of advanced disease has been made and from a site not previously irradiated. Alternatively, subjects must agree to have a biopsy taken prior to entering the study to provide adequate tissue. For the 1000 mg BID dose escalation cohort, subjects with melanoma, Merkel cell, MSI-H cancers, and cHL are not required to have archival or fresh biopsy tissue.

CCI

- 5) All persisting toxic effects of any prior antitumor therapy resolved to National Cancer Institute-Common Terminology Criteria for Adverse Events (NCI-CTCAE) version 5.0 Grade  $\leq 1$  or baseline before the first dose of study drug (with the exception of alopecia [Grade 1 or 2 permitted] and neurotoxicity [Grade 1 or 2 permitted]).
- 6) Eastern Cooperative Oncology Group (ECOG) Performance Status of  $\leq 2$
- 7) Life expectancy of  $\geq 3$  months, in the opinion of the investigator
- 8) Adequate organ function defined as follows:
  - a) Hematologic: Platelets  $\geq 100 \times 10^9/L$  ( $\geq 60 \times 10^9/L$  in subjects with HCC); Hemoglobin  $\geq 9.0$  g/dL; ANC  $\geq 1.5 \times 10^9/L$  (without blood transfusion, platelet transfusion, or growth factors within previous 7 days of the hematologic laboratory values obtained at screening visit)
  - b) Hepatic: AST/ALT  $\leq 2.5 \times$  upper limit of normal (ULN) (if liver metastases are present,  $\leq 5 \times$  ULN); total or conjugated bilirubin  $\leq 1.5 \times$  ULN
  - c) Renal: Creatinine clearance ( $CL_{cr}$ )  $\geq 45$  mL/min as calculated by the Cockcroft-Gault method

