**Table 5-4. Hepatic irAE Management Algorithm**

Hepatic irAEs		
CTCAE Grade of Liver Test Elevation	Management	Follow Up
Grade 1 AST or ALT > ULN to 3 × ULN or total bilirubin > ULN to 1.5 × ULN	Continue GS-4224 therapy per protocol	Continue liver function tests (LFT) monitoring per protocol. If worsens: Treat as Grade 2 or Grade 3-4.
Grade 2 AST or ALT > 3 to ≤ 5 × ULN or total bilirubin > 1.5 to ≤ 3 × ULN	Interrupt GS-4224 therapy per protocol Increase frequency of monitoring to every 3 days If subject has concurrent AST or ALT > 3 × ULN and total bilirubin > 2 × ULN, discontinue GS-4224 therapy per protocol.	If returns to baseline: Resume routine monitoring; resume GS-4224 therapy per protocol. If elevations persist > 5 to 7 days or worsen: 0.5-1 mg/kg/day methylprednisolone IV or oral equivalent. When LFT returns to Grade 1 or baseline, taper corticosteroids over ≥ 1 month, consider prophylactic antibiotics for opportunistic infections, and resume GS-4224 therapy per protocol.
Grade 3-4 AST or ALT > 5 × ULN and/or total bilirubin > 3 × ULN.	Discontinue GS-4224 therapy per protocol Increase frequency of monitoring to every 1-2 days 1-2 mg/kg/day methylprednisolone IV or oral equivalent.* Add prophylactic antibiotics for opportunistic infections Consult gastroenterology Consider obtaining MRI/CT scan of liver and liver biopsy if clinically warranted	If returns to Grade 2: Taper corticosteroids over ≥ 1 month. If does not improve in > 3 to 5 days, worsens or rebounds: Add mycophenolate mofetil 1 g twice daily. If no response within an additional 3-5 days, consider other immunosuppressants per local guidelines.

\* The recommended starting dose for Grade 4 hepatitis is 2 mg/kg/day methylprednisolone IV.  
 ALT alanine aminotransferase; AST aspartate aminotransferase; CT computed tomography; CTCAE Common Terminology Criteria for Adverse Events; irAE immune related adverse event; IV intravenous(ly); LFT liver function test; MRI magnetic resonance imaging; ULN upper limit of normal

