## 5.5. Prior and Concomitant Medications

### 5.5.1. Concomitant Medications

As of 30 March 2020, limited clinical drug-drug-interaction studies have been conducted with GS-4224.

In vitro data suggest that GS-4224 is a potential inhibitor of P-glycoprotein (P-gp), cytochrome P450 enzyme (CYP)2B6, CYP2C8, CYP2C9, CYP2C19, CYP3A, uridine diphosphate glucuronosyltransferase 1A1 (UGT1A1) and organic anion transporting polypeptide (OATP)1B1/3. In the absence of clinical data, administration of sensitive substrates of, or narrow therapeutic index drugs that are metabolized or transported by, these enzymes and transporters is not permitted from 14 days prior to the first dose of GS-4224, during the study period, and through the end of the follow-up visit, unless new data becomes available that would allow concomitant use of drugs described above during the study. Furthermore, in vitro data suggest that GS-4224 may be eliminated by metabolism with contribution by CYP3A and Sulfotransferase Family 2A Member 1 (SULT2A1), and may be a substrate of P-gp and breast cancer resistance protein (BCRP) transporters. In the absence of clinical data, administration of strong or moderate inhibitors or inducers of these enzymes and transporters is not permitted from 14 days prior to the first dose of GS-4224, during the study period, and through the end of the follow-up visit.

Examples of medications which are prohibited 14 days prior to the first dose of study drug, during the study period and through the end of the follow-up visit are listed in [Table 5-8](#). Administration of the listed medications may be permitted only if the study investigator deems it necessary for the treatment of a condition that emerges during the course of the study and with the approval of the medical monitor.

Preliminary data from a study that evaluated the effect of famotidine on the plasma exposures of GS-4224 indicated no clinically meaningful effect of acid-reducing agents on the PK of GS-4224. Based on these results, subjects can be allowed to concomitantly administer acid-reducing agents. It is recommended that subjects do not exceed the standard doses of the acid-reducing agents that are substrates for enzymes that are potentially inhibited by GS-4224 (eg, rabeprazole 20 mg once daily, lansoprazole 30 mg once daily, omeprazole 40 mg once daily, etc.).

Any medications not on the list should be reviewed with the sponsor prior to and during the study treatment period with GS-4224.

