7.2.1.1. Treatment-Emergent Laboratory Abnormalities

Treatment-emergent laboratory abnormalities are defined as values that increase at least 1 toxicity grade from baseline at any postbaseline time point, up to and including the date of last dose of study drug plus 30 days for subjects who permanently discontinued study drug, or the last available date in the database snapshot for subjects who were still on treatment at the time of an analysis. A baseline laboratory value will be defined as the last measurement obtained on or prior to the date/time of first dose of study drug. If the relevant baseline laboratory value is missing, any abnormality of at least Grade 1 observed within the time frame specified above will be considered treatment emergent.

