7.2.1.2. Summaries of Laboratory Abnormalities

The following summaries (number and percentage of subjects) for treatment-emergent laboratory abnormalities will be provided by lab test and cohort; subjects will be categorized according to the most severe postbaseline abnormality grade for a given lab test:

- TE laboratory abnormalities

In the summary of laboratory abnormalities, the denominator is the number of subjects with nonmissing postbaseline values up to 30 days after last dosing date.

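### Table 6-1 marks total bilirubin as a reflex test with no stated trigger, which conflicts with the hepatic, interruption and DLT rules that need it as a stand-alone value

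*Protocol*

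**What the plan says.** Protocol 6.2.9 makes the central laboratory responsible for chemistry as listed in Table 6-1. Appendix 2 schedules chemistry at screening, on Days 1, 4, 8, 11 and 15 of Cycle 1, on Day 1 of Cycles 2 to 5, every 3 weeks and at end of treatment, but names no analytes. Table 6-1 is therefore where the panel is defined.

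In its chemistry column the table prints "Total bilirubin b", and footnote b reads "Reflex testing based on other abnormalities". The row "Direct bilirubin" carries no marker. Footnote b also marks urine microscopy and the viral tests. No threshold or list of triggering results is given.

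Other sections use bilirubin as follows:
- **Table 5-4.** Total bilirubin is an alternative to AST/ALT in every row; Grade 2, for example, includes "or total bilirubin > 1.5 to ≤ 3 × ULN". Grade 3-4 joins the two with and/or.
- **Section 5.4.2.** Any drug-related laboratory abnormality of Grade 3 or higher leads to interruption. The stated exception is Grade 3 lymphopenia.
- **Section 3.2.1.1.** Non-hematologic toxicity of Grade 3 or higher is a DLT. The listed exceptions do not mention bilirubin.
- **Section 4.2, criterion 8b.** The limit of 1.5 × ULN applies to "total or conjugated bilirubin".

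For the analysis, SAP 7.2.1.2 summarises each laboratory test by cohort, and "the denominator is the number of subjects with nonmissing postbaseline values up to 30 days after last dosing date". SAP 7.2.1.1 adds: "If the relevant baseline laboratory value is missing, any abnormality of at least Grade 1 observed within the time frame specified above" counts as treatment-emergent.

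**The concern.** A test that runs only after some other abnormality cannot be relied on to find a rise that occurs alone, yet the hepatic table, the interruption rule and the general DLT item can all turn on such a rise. Because no trigger is stated, two sites or laboratories could follow the same table and test different subjects.

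Two things would be at stake if the footnote were applied literally. One is the DLT count, which is the primary endpoint and drives escalation in cohorts of 3 to 6. The other is the laboratory summary: the SAP's denominator would hold only subjects whose other results prompted the test, and its missing-baseline rule would apply to anyone not tested before dosing.

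**Working it through.** The plan states no bilirubin rate or other figure to reproduce. The check sets the passages side by side and then adds arithmetic with assumed inputs.

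**1. Does the schedule override the footnote?** No. Appendix 2 says when chemistry is drawn, and Table 6-1 says what chemistry contains. The footnote qualifies the entry in the second, so the two can both be followed with total bilirubin absent from a visit.

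**2. Which rules are exposed to an isolated rise?**
- Table 5-4: every row, since total bilirubin alone qualifies.
- Section 5.4.2: the general Grade 3 or higher laboratory item. The item that names bilirubin also needs a Grade 3 or 4 AST or ALT.
- DLT definition: mainly the general Grade 3 or higher non-hematologic item. The item that names bilirubin again needs a Grade 3 or 4 AST or ALT, which would be expected to prompt the reflex.
- Criterion 8b: only partly, because conjugated bilirubin is accepted and the direct fraction is unmarked.

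**3. Would the DLT-Evaluable Analysis Set catch the gap?** No. Protocol 8.3.1.4 and SAP 3.1.4 require the chemistry tests that the protocol specifies. Read literally, a subject without a total bilirubin result still meets that requirement and counts as free of DLT.

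**4. What does one missed DLT do under the 3+3 rules (Section 3.2.1)?**

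| Counted | True | Decision as counted | Decision if seen | Changed? |
|---|---|---|---|---|
| 0/3 | 1/3 | may escalate | enroll 3 more | yes |
| 1/6 | 2/6 | escalate, or eligible as MTD | de-escalate | yes |
| 0/6 | 1/6 | eligible as MTD | eligible as MTD | no |

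**5. Missing-baseline rule.** Take a subject steady at 1.4 × ULN. Criterion 8b admits that level, and Table 5-4 places it in Grade 1 (above ULN to 1.5 × ULN). With a baseline value, Grade 1 to Grade 1 is no increase and is not emergent. With no baseline value and a reflexed later test, the same level is counted as emergent.

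**6. Illustration of the denominator.** The 44 is the planned Phase 1b escalation size (Protocol 8.10). The other inputs are assumptions: 4 subjects with a true emergent rise, 25% to 75% of subjects ever reflex-tested (11 to 33), and 0, 2 or 4 of the rises isolated and so missed. The reported rate is (4 − missed) / tested. Routine testing gives 4/44 = 9.1%.

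| Tested | 0 missed | 2 missed | 4 missed |
|---|---|---|---|
| 11 | 4/11 = 36.4% | 2/11 = 18.2% | 0% |
| 22 | 4/22 = 18.2% | 2/22 = 9.1% | 0% |
| 33 | 4/33 = 12.1% | 2/33 = 6.1% | 0% |

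The reported rate can lie above, at or below 9.1%. The SAP summarises by cohort, so 44 is a convenient pooled figure and not the planned denominator. If total bilirubin was run with every panel, none of this arises.

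**The case against.** The best reply is that the marker is a slip. Total bilirubin sits in a scheduled panel, a routine direct fraction with a reflex total would be odd, and the adjacent unmarked row is direct bilirubin. Footnote b also fits poorly on the viral tests, which the same table ties to a history of infection. This is plausible, and it stands as a reason not to claim that total bilirubin went unmeasured. It does not remove the conflict, because a laboratory working from the table has only the printed instruction.

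Several stronger readings are tempting, but the documents do not support them:
- **Eligibility was compromised.** A subject can qualify on conjugated bilirubin. The Child-Pugh requirement for HCC does not help, since the protocol never lists its components.
- **The bilirubin DLT would be missed.** The item naming bilirubin needs raised transaminases as well. Section 3.2.1.1 also allows discussion of laboratory findings without a clear clinical correlate.
- **No isolated rise could be found.** GGT, alkaline phosphatase, LDH, direct bilirubin, urine bilirubin and urobilinogen are unmarked, and with no trigger defined any of them might prompt the test.
- **Any missed event changes escalation.** 0/6 against 1/6 does not.
- **No baseline would exist.** A subject who qualified on total bilirubin has a screening value, and SAP 7.2.1 lets local pre-dose results serve when no central result exists.
- **The SAP rate would be inflated.** The error can run either way.
- **The drug is expected to raise unconjugated bilirubin.** Section 5.5.1 lists "uridine diphosphate glucuronosyltransferase 1A1 (UGT1A1) and organic anion transporting polypeptide (OATP)1B1/3" among in vitro inhibition targets in order to restrict other medicines. It says nothing about bilirubin.

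It is also true that the SAP (Section 1) records early termination in Phase 1b with Phase 2 not started, so an edited footnote cannot change data already collected. The laboratory summaries are still to be produced, however, and subjects on study continue to be treated or followed.

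**Conclusion.** The concern holds as an internal inconsistency. Table 6-1 makes total bilirubin conditional on an undefined trigger, while Table 5-4, Section 5.4.2 and the general DLT item need it on its own. The passages must be reconciled.

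The consequences depend on the footnote having been followed as printed, which the documents do not settle. On that condition, an isolated rise may go undetected, some but not all 3+3 decisions could differ, and the total bilirubin summary would describe a selected subset under a baseline rule that can create events. The size is unknown; the span of 0% to 36.4% around 9.1% rests on assumed counts and shows only that neither direction can be ruled out. If total bilirubin was reported with every panel, the effect is nil and only the table needs correcting. A cheap correction to an operative instruction is worth making.

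**What to change.** - **Protocol Table 6-1.** Remove footnote b from total bilirubin so that it is reported with every chemistry panel scheduled in Appendix 2. If a fraction was meant to be reflexive, move the marker to direct bilirubin and state its trigger. Align the central laboratory manual. Criterion 8b, Table 5-4, Section 5.4.2 and the DLT definition keep their present thresholds.
- **CSR.** State whether total bilirubin was run routinely. If it was reflex-only, report by cohort how many subjects had a baseline value and how many had a postbaseline value, and flag events counted as emergent only because baseline was missing.

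The cost is one footnote and a matching line in the laboratory manual. The chemistry sample is already scheduled, so no extra draw is needed. The CSR step is a small count table and a flag built from existing data.
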